APPENDIX VI DRUGS TO BE AVOIDED OR USED WITH CAUTION**PROHIBITED MEDICATIONS**

Warfarin (Coumadin)
 Biologic agents
 Anticancer therapy
 Other investigational agents
 Steroid therapy for anti-neoplastic intent

CYP3A Strong Inhibitors

Atazanavir
 Clarithromycin
 Itraconazole
 Fluvoxamine
 Nefazodone
 Nelfinavir
 Ritonavir
 Saquinavir
 Telithromycin
 Voriconazole
 Ketoconazole
 Boceprevir
 Cobicistat
 Conivaptan

Indinavir
 Lopinavir
 Mibefradil
 Posaconazole
 Telaprevir
 Troleandomycin

CYP3A Moderate Inhibitors

Fluconazole
 Aprepitant
 Erythromycin
 Diltiazem
 Verapamil
 Amprenavir
 Atazanavir
 Ciprofloxacin
 Crizotinib
 Darunavir
 Dronedaron
 Fosamprenavir
 Imatinib
 Grapefruit juice

Seville orange juice

CYP3A Strong Inducers

Avasimibe
 Carbamazepine
 Mitotane
 Modafinil
 Phenobarbital
 Phenytoin
 Rifabutin
 Rifampin
 St. John's Wort

CYP3A Moderate Inducers

Bosentan
 Efavirenz
 Etravirine
 Modafinil
 Nafcillin
 Oxcarbazepine
 Troglitazone

MEDICATIONS TO USE WITH CAUTION**CYP3A Weak Inducers**

Armodafinil
 Clobazam
 Pioglitazone
 Glucocorticoids such as prednisone
 Rufinamide
 Nevirapine
 Pioglitazone
 Vemurafenib

CYP3A Weak inhibitors

Alprazolam
 Amlodipine
 Atorvastatin
 Cimetidine
 Ranitidine
 Amiodarone
 Bicalutamide
 Cilostazol
 Cyclosporine
 Fluvoxamine
 Fluoxetine
 Ginkgo

Goldenseal
 Isoniazid
 Nilotinib
 Oral contraceptives
 Pazopanib
 Ranitidine
 Ranolazine
 Suboxone
 Tipranavir
 Ticagrelor
 Zileuton

Note that this is not an exhaustive list. Further information can be found at the following websites:

<http://medicine.iupui.edu/clinpharm/ddis/main-table/>

and

<http://www.fda.gov/Drugs/DevelopmentApprovalProcess/DevelopmentResources/DrugInteractionsLabeling/ucm080499.htm>.

APPENDIX VII LUGANO REVISED RESPONSE CRITERIA FOR NON-HODGKIN LYMPHOMA 32

Site	PET-CT- Based Response	CT-Based Response
Complete Response	Complete metabolic response	Complete radiologic response (all of the following):
Lymph nodes & extralymphatic sites	Score 1, 2, or 3 with or without a residual mass on 5-point scale	Target nodes/nodal masses must regress \leq 1.5cm in longest transverse diameter of a lesion (LDi); no extralymphatic sites of disease
Non-measured lesion	NA	Absent
Organ enlargement	NA	Regress to normal
New Lesions	None	None
Bone Marrow	No evidence of FDG-avid disease in marrow	Normal by morphology; if indeterminate, and flow cytometry IHC negative
Partial Response	Partial metabolic response	Partial remission (all of the following):
Lymph nodes & extralymphatic sites	Score of 4 or 5 with reduced uptake compared with baseline and residual mass(es) of any size. No new or progressive lesions. At interim these findings suggest responding disease. At end of treatment these findings indicate residual disease.	\geq 50% decrease in SPD of up to 6 target measurable node & extranodal sites. When a lesion is too small to measure on CT, assign 5x5mm as the default value; when no longer visible, 0x0 mm. For a node >5x5mm, but smaller than normal, use actual measure for calculation.
Non-measured lesion	NA	Absent/normal, regressed but no increase
Organ enlargement	NA	Spleen must have regressed by >50% in length beyond normal
New lesions	None	None
Bone Marrow	Residual uptake higher than uptake in normal marrow but reduced compared with baseline (diffuse uptake compatible with reactive changes from chemotherapy allowed). If there are persistent focal changes in the marrow in the context of a nodal response, consideration should be given to further evaluation with MRI or biopsy or an interval scan.	NA

Abbreviations: CT, computed tomography; FDG, fluorodeoxyglucose; IHC, immunohistochemistry; LDi, longest transverse diameter of a lesion; MRI, magnetic resonance imaging; PET, positron emission tomography; PPD, cross product of the LDi and perpendicular diameter; SDi, shortest axis perpendicular
		

to the LDi; SPD, sum of the product of the perpendicular diameters for multiple lesions; NA, Not applicable		
Stable disease	No metabolic response	Stable Disease
Target nodes/nodal masses, extranodal lesions	Score 4 or 5 with no significant change in FDG uptake from baseline at interim or end of treatment	< 50% decrease from baseline in SPD of up to 6 dominant, measurable nodes and extranodal sites; no criteria for progressive disease are met
Non-measured lesion	NA	No increase consistent with progression
Organ enlargement	NA	No increase consistent with progression
New lesions	None	None
Bone Marrow	No change from baseline	NA
Progressive Disease	Progressive metabolic disease	One of the following:
Individual target nodes/nodal masses	Score 4 or 5 with an increase in intensity of uptake from baseline and/or nadir with evidence of new or enlarging FDG avid nodes.	PPD progression: An individual node/lesion must be: 
 • LDi > 1.5 cm and • Increase by $\geq 50\%$ from PPD nadir and • Increase in LDi or SDi from nadir 
 - 0.5 cm for lesions ≤ 2 cm - 1.0 cm for lesions > 2 cm
Extranodal lesions	New FDG-avid foci consistent with lymphoma at interim or end-of-treatment assessment	
 • In the setting of splenomegaly, the splenic length must increase by > 50% of the extent of its prior increase beyond baseline. If no prior splenomegaly, must increase by at least 2 cm from baseline • New or recurrent splenomegaly
Non-measured lesions	None	New or clear progression of preexisting non-measured lesions
New lesions	New FDG-avid foci consistent with lymphoma rather than another etiology (e.g., infection, inflammation). If uncertain regarding etiology of new lesions, biopsy or interval scan may be considered	Regrowth of previously resolved lesions A new node > 1.5 cm in any axis A new extranodal site > 1.0 cm in any axis; if < 1.0 cm in any axis, its presence must be unequivocal and must be attributable to lymphoma Assessable disease of any size unequivocally attributable to lymphoma
Bone Marrow	New or recurrent FDG-avid foci	New or recurrent involvement

***PET 5-point scale**

1-No uptake above background

2-Uptake \leq mediastinum

3-Uptake > mediastinum but \leq liver

4-Uptake moderately > liver

5-Uptake markedly higher than liver and/or new lesions

X-New areas of uptake unlikely to be related to lymphoma

APPENDIX VIII RECOMMENDATIONS FOR INITIAL MANAGEMENT OF ELECTROLYTE

ABNORMALITIES AND PREVENTION OF TUMOR LYSIS SYNDROME

- Within the first 24 hours after either the first dose or dose increase, if any laboratory criteria below are met, the patient should be hospitalized for monitoring and the investigator notified. No additional study drugs doses should be administered until resolution. A rapidly rising serum potassium level is a medical emergency.
- Nephrology (or acute dialysis service) must be consulted/contacted on admission (per institutional standards to ensure emergency dialysis is available).
- Intravenous (IV) fluids (e.g. D5 ½ normal saline) should be initiated at a rate of at least 1 mL/kg/h rounded to the nearest 10 mL (target 150 to 200 mL/h; not < 50 mL/h). Modification of fluid rate should also be considered for individuals with specific medical needs.
- Monitor for symptoms or signs of tumor lysis syndrome (TLS; e.g. fever, chills, tachycardia, nausea, vomiting, diarrhea, diaphoresis, hypotension, muscle aches, weakness, paresthesias, mental status changes, confusion, and seizures). If any clinical features are observed, recheck potassium, phosphorous, uric acid, calcium and creatinine within 1 hour.
- Vital signs should be taken at time of all blood draws or any intervention
- The management recommendations below focus on the minimum initial response required. If a diagnosis of TLS is established, ongoing intensive monitoring and multi-disciplinary management will be as per institutional protocols.

Abnormality	Management Recommendations
Hyperkalemia (including rapidly rising potassium)	
Potassium \geq 0.5 mmol/L increase from prior value (even if potassium within normal limits [WNL])	
Recheck potassium, phosphorus, uric acid, calcium and creatinine in 1 hour STAT. If further \geq 0.2 mmol/L increase in potassium, but still < upper limit of normal (ULN), manage as per potassium \geq ULN. Otherwise recheck in 1 hour.
 
Resume per protocol testing if change in potassium is < 0.2 mmol/L, and potassium < ULN, and no other evidence of tumor lysis.
 
At the discretion of the investigator, may recheck prior to hospitalization. If stable or decreased, and still WNL, hospitalization is at the discretion of the investigator. Potassium, phosphorus, uric acid, calcium and creatinine must be rechecked within 24 hours.

Potassium > upper limit of normal	
Perform STAT ECG and commence telemetry.
 
Nephrology (or other acute dialysis service) notification with consideration of initiating dialysis.
 
Administer Kayexalate 60 g (or Resonium A 60 g).
 
Administer furosemide 20 mg IV \times 1.
 
Administer calcium gluconate 100 to 200 mg/kg IV slowly if there is ECG/telemetry evidence of life threatening arrhythmias.
 
Recheck potassium, phosphorus, uric acid, calcium and creatinine in 1 hour STAT.
 
If potassium < ULN 1 hour later, repeat potassium, phosphorus, uric acid, calcium and creatinine 1, 2 and 4 hours, if no other evidence of tumor lysis.

Hyperkalemia (including rapidly rising potassium) (continued)	
Potassium \geq 6.0 mmol/L (6.0 mEq/L) and/or symptomatic (e.g., muscle cramps, weakness, paresthesias, nausea, vomiting, diarrhea)	
Perform STAT ECG and commence telemetry.
 
Nephrology (or other acute dialysis service) assessment with consideration of initiating dialysis.
 
Administer Kayexalate 60 g (or Resonium A 60 g).
 
Administer furosemide 20 mg IV \times 1.
 
Administer insulin 0.1 U/kg IV + D25 2 mL/kg IV.
 
Administer sodium bicarbonate 1 to 2 mEq/kg IV push.
 
If sodium bicarbonate is used, rasburicase should not be used as this may exacerbate calcium phosphate precipitation.
 
Administer calcium gluconate 100 to 200 mg/kg IV slowly if there is ECG/telemetry evidence of life threatening arrhythmias. Do not administer in same IV line as sodium bicarbonate.
 
Recheck potassium, phosphorus, uric acid, calcium and creatinine every hour STAT.

Hyperuricemia	
Uric acid \geq 8.0 mg/dL (476 μ mol/L)	
Consider rasburicase (dose based on local guidelines and/or institutional standards).
 
If rasburicase is used, sodium bicarbonate should not be used as this may exacerbate calcium phosphate precipitation.
 
Recheck potassium, phosphorus, uric acid, calcium and creatinine in 1 hour STAT.

Uric acid \geq 10 mg/dL (595 μ mol/L)	
Administer rasburicase (dose based on local guidelines and/or institutional standards).
 
When rasburicase is used, sodium bicarbonate should not be used as this may exacerbate calcium phosphate precipitation.

OR Uric acid \geq 8.0 mg/dL (476 μ mol/L) with 25% increase and creatinine increase \geq 0.3 mg/dL (\geq 0.027 mmol/L) from pre-dose level	
Notify nephrology (or other acute dialysis service).
 
Recheck potassium, phosphorus, uric acid, calcium and creatinine in 1 hour STAT.
 
If uric acid $<$ 8.0 mg/dL 1 hour later, repeat potassium, phosphorus, uric acid, calcium and creatinine 2 and 4 hours, later, if no other evidence of tumor lysis.

Hypocalcemia	
Calcium \leq 7.0 mg/dL (1.75 mmol/L) AND Patient symptomatic (e.g., muscle cramps, hypotension, tetany, cardiac arrhythmias)	
Administer calcium gluconate 50 to 100 mg/kg IV slowly with ECG monitoring.
 
Telemetry.
 
Recheck potassium, phosphorus, uric acid, calcium and creatinine in 1 hour STAT.
 
If calcium normalized 1 hour later, repeat potassium, phosphorus, uric acid, calcium and creatinine 2 and 4 hours, later, if no other evidence of tumor lysis.
 
Calculate corrected calcium and check ionized calcium if albumin low.

Hyperphosphatemia	
Phosphorus \geq 5.0 mg/dL (1.615 mmol/L) with \geq 0.5 mg/dL (0.16 mmol/L) increase	
Administer a phosphate binder (e.g., aluminum hydroxide, calcium carbonate, sevelamer hydroxide, or lanthanum carbonate).
 
Nephrology (or other acute dialysis service) notification (dialysis required for phosphorus \geq 10 mg/dL).
 
Recheck potassium, phosphorus, uric acid, calcium and creatinine in 1 hour STAT.
 
If phosphorus $<$ 5.0 mg/dL 1 hour later, repeat potassium, phosphorus, uric acid, calcium and creatinine 2 and 4 hours, later, if no other evidence of tumor lysis.

Creatinine	
Increase \geq 25% from baseline	
Start or increase rate of IV fluids.
 
Recheck potassium, phosphorus, uric acid, calcium and creatinine in 1 to 2 hours STAT.

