APPENDIX IX DEFINITIONS OF LABORATORY AND CLINICAL TUMOR LYSIS SYNDROME

Metabolic Abnormality	Criteria for Classification of Laboratory Tumor Lysis Syndrome	Criteria for Classification of Clinical Tumor Lysis Syndrome
Hyperuricemia	Uric acid > 8.0 mg/dL (475.8 μ mol/liter) in adults or above the upper limit of the normal range for age in children	
Hyperphosphatemia	Phosphorus > 4.5 mg/dL (1.5 mmol/liter) in adults or > 6.5 mg/dL (2.1 mmol/liter) in children	
Hyperkalemia	Potassium > 6.0 mmol/liter	Cardiac dysrhythmia or sudden death probably or definitely caused by hyperkalemia
Hypocalcemia	Corrected calcium < 7.0 mg/dL (1.75 mmol/liter) or ionized calcium < 1.12 (0.3 mmol/liter) [†]	Cardiac dysrhythmia, sudden death, seizure, neuromuscular irritability (tetany, paresthesias, muscle twitching, carpopedal spasm, Trousseau's sign, Chvostek's sign, laryngospasm, or bronchospasm), hypotension, or heart failure probably or definitely caused by hypocalcemia
Acute kidney injury [‡]	Not applicable	Increase in the serum creatinine level of 0.3 mg/dL (26.5 μ mol/liter) (or a single value > 1.5 times the upper limit of the age-appropriate normal range if no baseline creatinine measurement is available) or the presence of oliguria, defined as an average urine output < 0.5 mL/kg/hr for 6 hrs

[†] The corrected calcium level in milligrams per deciliter = measured calcium level in milligrams per deciliter + $0.8 \times (4\text{-albumin in grams per deciliter})$.

[‡] Acute kidney injury is defined as an increase in the creatinine level of at least 0.3 mg per deciliter (26.5 μ mol per liter) or a period of oliguria lasting 6 hours or more. By definition, if acute kidney injury is present, the patient has clinical tumor lysis syndrome. Data about acute kidney injury from Levin et al.

Note: In laboratory tumor lysis syndrome, two or more metabolic abnormalities must be present during the same 24-hour period within 3 days before the start of therapy or up to 7 afterward. Clinical tumor lysis syndrome requires the presence of laboratory tumor lysis syndrome plus an increased creatinine level, seizures, cardiac dysrhythmia, or death.

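### Appendix VIII's 24-hour triggers can miss one laboratory-TLS pair (phosphorus with asymptomatic low calcium), Appendix IX gives two answers on kidney injury, and three TLS cross-references are wrong

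*Combined protocol and SAP*

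**What the plan says.** **Trigger (Appendix VIII, first bullet).** The window is "Within the first 24 hours after either the first dose or dose increase". In that window, "if any laboratory criteria below are met, the patient should be hospitalized for monitoring and the investigator notified", and neither study drug is given again until resolution. Two rows carry an extra condition. The calcium row (7.0 mg/dL or lower) also requires "Patient symptomatic (e.g., muscle cramps, hypotension, tetany, cardiac arrhythmias"). The phosphorus row requires at least 5.0 mg/dL together with a rise of at least 0.5 mg/dL. The creatinine row is a rise of at least "25% from baseline". For established TLS, Appendix VIII adds: "If a diagnosis of TLS is established, ongoing intensive monitoring and multi-disciplinary management will be as per institutional protocols".

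**Definition (Appendix IX).** Laboratory TLS is any two of four abnormalities in the same 24 hours. One is "Phosphorus > 4.5 mg/dL (1.5 mmol/liter) in adults", with no rise required. Another is corrected calcium below 7.0 mg/dL, with no symptoms required. On kidney injury (a creatinine rise of at least 0.3 mg/dL, or oliguria), the footnote says: "By definition, if acute kidney injury is present, the patient has clinical tumor lysis syndrome". The closing Note makes laboratory TLS a requirement for clinical TLS.

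**Dose rules (section 5.3.1).** For electrolyte changes that suggest TLS, the next venetoclax dose is held. Venetoclax resumes at the same dose if the changes resolve within 24 to 48 hours of the last dose. It resumes 100 mg lower if they take longer, or after clinical TLS.

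**Pointers.** Sections 5.3.1 and 5.3.2 send TLS management to Appendix VII, and section 5.3.1 places the TLS definitions in Appendix VIII.

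**The concern.** Appendix VIII describes its actions as the minimum initial response. One would expect that minimum to reach any patient who meets the protocol's own definition of laboratory TLS. If it does not, an outpatient whose 8-hour sample meets the definition may be left to local judgment on admission and on a 1-hour recheck, and ibrutinib may continue.

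The two statements on kidney injury matter because clinical TLS carries a dose consequence. If they disagree, two of the three centers could restart venetoclax at different doses on identical laboratory values. They could also report the event differently, since section 13.4.5 asks for both serious and non-serious TLS to go to the venetoclax manufacturer.

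The pointers matter because a clinician who follows sections 5.3.1 or 5.3.2 to Appendix VII arrives at the Lugano response criteria, not at TLS management.

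**Working it through.** The plan states no figure on this point, so there is nothing to reproduce. The check sets the rules side by side.

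**Step 1. Limits compared.**

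| Abnormality | Appendix IX (laboratory TLS) | Appendix VIII row | Always covered? |
|---|---|---|---|
| Uric acid | > 8.0 mg/dL | ≥ 8.0 mg/dL | Yes |
| Potassium | > 6.0 mmol/L | ≥ 6.0 mmol/L | Yes |
| Phosphorus | > 4.5 mg/dL | ≥ 5.0 mg/dL and rise ≥ 0.5 mg/dL | No |
| Corrected calcium | < 7.0 mg/dL | ≤ 7.0 mg/dL and symptoms | No |

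Combinations of two or more of the four: 6 pairs + 4 triples + 1 set of four = 11. Any combination with uric acid or potassium meets a row. Only phosphorus + calcium contains neither, so 10 of 11 are always covered and one can be missed.

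**Step 2. The missed case.** Take phosphorus 4.0 to 4.8, corrected calcium 6.8, no symptoms, and potassium, uric acid and creatinine unchanged.
- Appendix IX: 4.8 > 4.5 and 6.8 < 7.0, so two abnormalities and laboratory TLS.
- Appendix VIII: 4.8 < 5.0 and no symptoms, so no row is met.

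The open phosphorus band is 5.0 − 4.5 = 0.5 mg/dL. Phosphorus of 5.0 or more with a rise below 0.5 also misses its row. Its pre-dose value must then have exceeded 5.0 − 0.5 = 4.5, so that abnormality was already present before dosing and only the calcium is new.

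**Step 3. Creatinine row against the kidney-injury limit.** A 0.3 mg/dL rise equals 25% at a baseline of 0.3 / 0.25 = 1.2 mg/dL. Above that baseline it falls short of the row: 0.3/1.3 = 23.1%, 0.3/1.4 = 21.4%, 0.3/1.5 = 20.0%. Such patients can be eligible (creatinine clearance of at least 50 mL/min). For an assumed man aged 60 weighing 80 kg with creatinine 1.4, Cockcroft-Gault gives (140 − 60) × 80 / (72 × 1.4) = 63.5 mL/min.

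**Step 4. The two kidney-injury statements.** Take phosphorus 4.2 to 5.2, creatinine 1.0 to 1.3 (+0.3, or 30%), other values normal, resolved 36 hours after the last dose. This is one metabolic abnormality, so not laboratory TLS, plus kidney injury.

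| Reading | Clinical TLS? | Restart from 400 mg | Restart from 600 mg |
|---|---|---|---|
| Footnote | Yes | 300 mg | 500 mg |
| Note | No | 400 mg | 600 mg |

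The step is 100/400 = 25% or 100/600 = 16.7%. The conflict decides it only if the change resolves within 48 hours, because a longer change brings the reduction anyway. Appendix VIII foresees this kind of patient: one uric acid row is 8.0 mg/dL or more "with 25% increase and creatinine increase" of at least 0.3 mg/dL.

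**Step 5. Pointers.** By their own headings, Appendix VII is the Lugano criteria, VIII is TLS management and IX is the TLS definitions. Each of the three references is one too low.

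**The case against.** The best reply is that Appendix VIII lists early-action recommendations while Appendix IX is a classification, and nothing requires one to contain the other. The missed patient is also not unattended. Section 5.3.1 requires prompt review of results, holds venetoclax and calls for aggressive management. Section 6.2 may stop both drugs if the event is graded 3 or higher, and section 1.7.2 reports laboratory TLS at Grade 3. Patients with a node of 8 cm or more, or circulating lymphoma cells, are already inpatients for the first dose.

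Most of this stands, and it limits the weight of the point. It does not close the gap. The section 5.3.1 management pointer, once corrected, leads to the same table that lacks a row for this patient. The dose bullet holds venetoclax only. Institutional protocols give no common rule across three centers.

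On creatinine, the man in step 3 has a clearance below 80 mL/min (63.5; at creatinine 1.2 it would be 6400 / (72 × 1.2) = 74.1), and section 5.3.2 already says hospitalization should be considered for such patients. That is fair, but it is discretionary.

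On kidney injury, the Note can be read as a prerequisite for the footnote, though the text does not say so. In the first 24 hours the step 4 patient meets the phosphorus and creatinine rows, so admission and the drug hold are the same under either reading. An admission beyond 24 hours is a serious adverse event and is reported regardless. What remains is the 100 mg step and the event label.

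Two stronger readings are tempting. A reader might infer that, because Appendix IX counts laboratory TLS for 7 days after the start of therapy, a 24-hour trigger leaves most of that period uncovered. The documents do not support this as a measure of the gap: scheduled chemistry after the first dose falls at 8 and 24 hours (also 12 for inpatients) and then on Day 8 ± 1, so nearly all first-week samples lie inside the trigger window. A reader might also infer that the ionized-calcium limit widens the gap, but ionized calcium is not a scheduled test.

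**Conclusion.** The point holds, at the lowest severity. On the literal text, one of 11 laboratory-TLS combinations can meet no Appendix VIII row, within a phosphorus band 0.5 mg/dL wide and only in a patient without symptoms whose other rows are quiet. On the first dose this concerns outpatients. Appendix IX gives opposite answers for kidney injury with a single metabolic abnormality, worth one 100 mg venetoclax step when electrolytes recover within 48 hours. Three cross-references are wrong.

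A reader might infer that patients in the gap go untreated. The documents do not support that, because section 5.3.1 still holds venetoclax and calls for aggressive management. A reader might also infer that an isolated creatinine rise would cut the dose under the footnote. That is doubtful, because the section 5.3.1 dose rules are introduced for electrolyte changes.

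The conclusion assumes that Appendix VIII rows are applied as printed. The documents give no frequency for these cases, and section 1.8.1.1 describes TLS risk as low in non-CLL subjects.

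**What to change.** 1. Appendix VIII, first bullet, keeping its 24-hour window, add: *A patient who newly meets Appendix IX laboratory TLS relative to pre-dose values is managed as meeting a listed criterion, with potassium, phosphorus, uric acid, calcium and creatinine rechecked in 1 hour STAT.* Change the creatinine row to *≥ 25% or ≥ 0.3 mg/dL increase from baseline*, so that a rise such as 1.4 to 1.7 is also managed.
2. Appendix IX footnote, replace the by-definition sentence with: *Acute kidney injury is clinical TLS when laboratory TLS is also present.* On its own this would choose the less cautious dosing. So extend the third dose bullet of section 5.3.1, after the reference to clinical TLS, with: *or electrolyte changes suggestive of TLS with acute kidney injury as defined in Appendix IX.* The step 4 patient then resumes 100 mg lower at every center.
3. Sections 5.3.1 and 5.3.2: TLS management is in Appendix VIII, not VII. Section 5.3.1: the TLS definitions are in Appendix IX, not VIII.

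The cost is a few sentences, one row limit and three appendix numbers, with no new scheduled test. The downside is a rare extra admission or recheck, and a 100 mg venetoclax reduction in a rare patient with one electrolyte change plus kidney injury.
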